4.3.7.2. Analysis Methods

Descriptive statistics of actual values and changes from baseline by treatment group will be provided at each time point during double-blind induction phase. A frequency distribution will also be provided for GAD-7 severity categories at each time point. Graphical presentations will also be provided.

The change from baseline in GAD-7 total score over time in the double-blind induction phase will be analyzed using the same MMRM as described in Section 4.2.3.1 for primary efficacy endpoint, with the covariate “baseline MADRS total score” changed to “baseline GAD-7 total score”.

4.3.8. MADRS

4.3.8.1. Definition

The definition of MADRS is in section 4.2.1.

4.3.8.2. Analysis Methods

Descriptive statistics of actual values and changes from baseline will be summarized at each time point for each phase (DB induction, DB follow-up, PT, OL induction and OL follow-up). The total score as well as the individual item scores will be summarized separately. Graphical presentations will also be provided.

5. SAFETY

All safety summaries for induction phases will be based on the safety analysis sets described in Section 2.4.3. Safety summaries for the follow-up phases will be based on the follow-up analysis sets described in Section 2.4.4.

Unless specified otherwise, Baseline (DB) will be used for DB induction phase and DB follow-up phase. Baseline (OL) will be used for OL induction phase and OL follow-up phase.

5.1. Adverse Events

The Medical Dictionary for Regulatory Activities (MedDRA) (version 20.0 or above) will be used to classify adverse events (AEs) by system organ class and preferred term. Treatment-emergent adverse events (TEAEs) that occurred in each analysis phase (DB induction, DB follow-up, PT, OL induction, OL follow-up) will be summarized by system organ class and preferred term.

The number (%) of subjects with TEAEs, serious TEAEs (SAEs), and TEAEs that led to study drug discontinuation, dose reduction will be summarized by system organ class and preferred term. TEAEs will be summarized by onset time (4 week intervals). Data listings will be generated for deaths, other SAEs, and discontinuations due to AEs.

A TEAE is an event that is new in onset or increased in severity following treatment initiation. An event that starts prior to, and ends after the initiation of study medication will be considered treatment-emergent only if the severity increases after the start of medication.

Treatment-emergent adverse events (TEAEs) are defined as follows for each analysis phase:

- TEAEs in DB induction phase:
 - a. If AE onset time is not missing: DB start date/time \leq AE onset date and time \leq DB end date
 - b. If AE onset time is missing: DB start date \leq AE onset date \leq DB end date
- TEAEs in OL induction phase:
 - a. If AE onset time is not missing: OL start date/time \leq AE onset date and time \leq OL end date
 - b. If AE onset time is missing: OL start date \leq AE onset date \leq OL end date
- AEs in DB follow-up phase: DB FU start date \leq AE onset date \leq DB FU end date
- AEs in OL follow-up phase: OL FU start date \leq AE onset date \leq OL FU end date

- For the AEs that have both day and month missing, treatment-emergent flag is assigned based on the rules presented in Section 2.6.

In addition, TEAEs will be summarized by severity and relationship to study medication using the preferred term. For the summaries of TEAEs by severity/relationship to study medication, the observation with the most severe occurrence/closest relationship to study medication will be chosen if there is more than one incident of an AE reported during the analysis phase by the subject.

Adverse Events of Special Interest

Clinically relevant TEAEs of special interest will be examined separately grouped in the following categories:

- Suggestive of abuse potential (Aggression, Confusional state, Decreased activity, Dependence, Disorientation, Dissociation, Dissociative disorder, Dizziness, Drug abuse, Drug abuser, Drug dependence, Drug use disorder, Drug detoxification, Drug diversion, Drug rehabilitation, Drug tolerance, Drug tolerance increased, Drug withdrawal convulsions, Drug withdrawal headache, Drug withdrawal syndrome, Euphoric mood, Feeling abnormal, Feeling drunk, Feeling of relaxation, Hallucination, Hallucination, auditory, Hallucination, gustatory, Hallucination, olfactory, Hallucination, synaesthetic, Hallucination, tactile, Hallucination, visual, Hallucinations, mixed, Inappropriate affect, Mental impairment, Product tampering, Psychomotor hyperactivity, Psychotic disorder, Rebound effect, Somatic hallucination, Somnolence, Substance abuser, Substance dependence, Substance use, Substance use disorder, Substance-induced mood disorder, Substance-induced psychotic disorder, Thinking abnormal, Withdrawal arrhythmia, Withdrawal syndrome)
- increased blood pressure (Blood pressure increased, Blood pressure diastolic increased, Blood pressure systolic increased, Hypertensive crisis, Hypertensive emergency, Hypertension)
- increased heart rate (Heart rate increased, Tachycardia, Extrasystoles)
- transient dizziness/vertigo (Dizziness, Dizziness exertional, Dizziness postural, Procedural Dizziness, Vertigo, Vertigo labyrinthine, Vertigo positional, Vertigo CNS origin);
- impaired cognition (Cognitive disorder);
- cystitis (Allergic cystitis, Chemical cystitis, Cystitis, Cystitis erosive, Cystitis haemorrhagic, Cystitis interstitial, Cystitis noninfective, Cystitis ulcerative, Cystitis-like symptom, Pollakiuria, Dysuria, Micturition urgency, Nocturia);
- anxiety (Anticipatory anxiety, Anxiety, Anxiety disorder, Agitation, Fear, Feeling jittery, Irritability, Nervousness, Panic attack, Tension).

The number and percentage of subjects taking concomitant medication for dissociation events (preferred term of Dissociation) at any time during each induction phase will be provided.

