6.4. Posttreatment Phase

Subjects who relapse within 20 weeks after the start of the posttreatment phase will transit to an OL induction phase and receive 4 weeks of OL treatment course with intranasal esketamine. Subjects who meet the criteria of relapse, they need to join OL induction phase before next remote MADRS assessment. Subjects who relapse more than 20 weeks after the start of the posttreatment phase will withdraw from the study and clinical/standard-of-care treatment will be arranged by the study investigator after relapse. Subjects who have no relapse throughout this 24-week posttreatment phase will complete this study without 4-week follow-up phase. The oral antidepressant must be continued at a stable dose during post treatment phase.

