11.8. Safety Analyses

Safety analysis set will consist of all randomized subjects who receive at least 1 dose of intranasal study drug in the double-blind induction phase. Safety data for the double-blind period will be analyzed for this population. For the analysis of safety data in the OL induction phase, all subjects who received at least 1 dose of intranasal study drug in this period will be analyzed.

Adverse Events

For each AE, the number of subjects who experience at least 1 occurrence of the given event will be summarized by treatment group.

The verbatim terms used in the eCRF by investigators to identify AEs will be coded using the Medical Dictionary for Regulatory Activities (MedDRA). The TEAEs are AEs with onset during the treatment phase or that are a consequence of a preexisting condition that has worsened since baseline. All reported AEs will be included in the analysis. For each AE, the percentage of subjects who experience at least 1 occurrence of the given event will be summarized by treatment group. In addition, comparisons between treatment groups will be provided if appropriate.

The TEAEs of special interest will be examined separately (please refer to Section 3.2.6). The AEs of special interest will be further listed in the SAP.

Summaries, listings, datasets, or subject narratives may be provided, as appropriate, for those subjects who die, who discontinue treatment due to an AE, or who experience a severe or an SAE.

Clinical Laboratory Tests

Laboratory data will be summarized by type of laboratory test. Markedly abnormal results (specified in the SAP) will be used in the summary of laboratory data. Descriptive statistics will be calculated for each laboratory analyte at each respective scheduled time point in each phase of the study. Changes from baseline results will be presented. Frequency tabulations of the abnormalities will be made. A listing of subjects with any markedly abnormal laboratory results will also be provided.

Electrocardiogram (ECG)

The effects on cardiovascular variables will be evaluated by means of descriptive statistics and frequency tabulations. These tables will include observed values and changes from baseline values.

Electrocardiogram data will be summarized by ECG parameter. Descriptive statistics will be calculated at baseline and for observed values and changes from baseline at each scheduled time point. Frequency tabulations of the abnormalities will be made.

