2.1.2. Analysis Phase Start and End Dates

Double-blind Induction Phase

The start date of the double-blind induction phase (referred to as ‘DB start date’) is the date of the first dose of intranasal study medication. The double-blind induction phase end date (referred to as ‘DB end date’) is the maximum of the date of the last visit in the double-blind induction phase and the date of completion/withdrawal from the double-blind induction phase.

The start date/time of the double-blind induction phase (referred to as, ‘DB start date/time’) is the DB start date and the time of the first dose of intranasal study medication.

Double-blind Follow-up Phase

The start date of the double-blind follow-up phase (referred to as ‘DB FU start date’) is the day after the DB end date. The double-blind follow-up phase end date (referred to as ‘DB FU end date’) is the maximum of the last DB follow-up visit date or the end of trial date.

Posttreatment Phase

The start date of the posttreatment phase (referred to as ‘PT start date’) is the day after the DB end date. The posttreatment phase end date (referred to as ‘PT end date’) is defined as: for subjects who entered OL phase, the day of OL start date (defined below); for subjects who did not enter OL, including responders who withdraw within 4 weeks after the last dose of DB intranasal drug, the maximum of the last posttreatment visit date or the end of trial date.

For subjects who entered OL phase, PT end date/time is one minute before OL start date/time (defined below).

Open-Label Induction Phase

The start date of the open-label induction phase (referred to as ‘OL start date’) is the date of the first dose of intranasal study medication in a second induction treatment course. The open-label induction phase end date (referred to as ‘OL end date’) is the maximum of the date of the last visit in the open-label induction phase and the date of completion/withdrawal from the open-label induction phase.

The start date/time of the open-label induction phase (referred to as, ‘OL start date/time’) is the OL start date and the time of the first dose of intranasal study medication in the second induction treatment course.

Open-Label Follow-up Phase

The start date of the open-label follow-up phase (referred to as ‘OL FU start date’) is the day after the OL end date. The open-label follow-up phase end date (referred to as ‘OL FU end date’) is the maximum of the last OL follow-up visit date or the end of trial date.

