2.6. Imputation Rules for Missing Adverse Event (AE) Dates

Treatment-emergent adverse events (TEAEs) are those events with an onset date/time on or after the start of study medication during induction phase (DB/OL), and occurred on or before the end of the corresponding induction phases (DB/OL). Adverse events (AEs) for the follow-up (DB/OL) phase are those events with an onset date on or after the start of the follow-up (DB/OL) phase, and occurred on or before the end of the follow-up (DB/OL) phase. Adverse events (AEs) for the posttreatment phase are those events with an onset date on or after the start of the posttreatment phase, and occurred on or before the end of the posttreatment phase. A conservative approach will be used to handle the missing dates for adverse events.

Onset Date

If the onset date of an AE is missing day only, it will be set to:

1. First day of the month that the AE occurred, if month/year of the onset of AE is different than the month/year of DB start date
2. The day of DB start date, if the month/year of the onset of AE is the same as month/year of the DB start date and month/year of the AE resolution date is different
3. The day of DB start date or day of AE resolution date, whichever is earliest, if month/year of the onset of AE and month/year of the DB start date and month/year of the AE resolution date are the same.

If the onset date of an AE is missing both day and month, it will be set to the earliest of:

1. January 1 of the year of onset, as long as this date is after the DB start date.
2. One day after the DB start date, if this date is the same year that the AE occurred.
3. The day of AE resolution date, if this date is the same year that the AE occurred.

A completely missing onset date of an adverse event will be set to the day of DB start date or day of AE resolution date, whichever is earliest.

Similar rules will be applied for OL missing onset date.

Resolution Date

The missing day of resolution of an AE will be set to the last day of the month of resolution.

If the resolution date of an AE is missing both day and month, it will be set to the earlier of the date of withdrawal, study completion, or December 31 of the year.

A completely missing resolution date of an AE that is not recorded as ongoing will be set to the date of study completion/discontinuation.

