5.5. Other Safety Parameters

5.5.1. Columbia Suicide Severity Rating Scale (C-SSRS)

The C-SSRS (Columbia Suicide Severity Rating Scale) is a low-burden measure of the spectrum of suicidal ideation and behavior that was developed in the National Institute of Mental Health Treatment of Adolescent Suicide Attempters Study to assess severity and track suicidal events through any treatment.⁹ It is a semi structured clinician-administered questionnaire designed to solicit the occurrence, severity, and frequency of suicide-related ideation and behaviors during the assessment period. Using the C-SSRS, potentially suicide-related events will be categorized using the following scores:

Suicidal Ideation (1-5)

1. Wish to be Dead
2. Non-specific Active Suicidal Thoughts
3. Active Suicidal Ideation with Any Methods (Not Plan) without Intent to Act
4. Active Suicidal Ideation with Some Intent to Act, without Specific Plan
5. Active Suicidal Ideation with Specific Plan and Intent

Suicidal Behavior (6-10)

6. Preparatory Acts or Behavior
7. Aborted Attempt
8. Interrupted Attempt
9. Actual Attempt (non-fatal)
10. Completed Suicide

If no events qualify for a score of 1 to 10, a score of 0 will be assigned (0= “no event that can be assessed on the basis of C-SSRS”). Higher scores indicate greater severity.

The summaries of the C-SSRS outcomes will be applied for subjects who have at least 1 postbaseline C-SSRS measurement and a pretreatment C-SSRS assessment (assessment at Baseline visit).

A frequency distribution at each scheduled time point will be provided. Shifts from the baseline visit to the most severe/maximum score during each analysis phase (DB induction, DB follow-up, PT, OL induction and OL follow-up) will be summarized.

The maximum score assigned for each subject will also be summarized into one of three broad categories: No suicidal ideation or behavior (0), Suicidal ideation (1-5), Suicidal behavior (6-10). Shifts from the baseline visit to the maximum category during each analysis phase will be summarized.

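### Posttreatment adverse events are summarised as crude percentages although the observation window depends on relapse; exposure-adjusted rates and at-risk denominators would be a cheap addition

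*SAP*

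**What the plan says.** SAP 5.1 states that treatment-emergent AEs "that occurred in each analysis phase (DB induction, DB follow-up, PT, OL induction, OL follow-up) will be summarized by system organ class". The measure is a count with a percentage: "The number (%) of subjects with TEAEs, serious TEAEs (SAEs), and TEAEs that led to study drug discontinuation". Protocol 11.8 likewise says that for each AE "the percentage of subjects who experience at least 1 occurrence of the given event will be summarized by treatment group", and allows comparisons between groups where suitable.

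The PT window is set elsewhere. SAP 2.6 gives the opening rule: "Adverse events (AEs) for the posttreatment phase are those events with an onset date on or after the start of the posttreatment phase". SAP 2.1.2 starts PT on the day after the double-blind (DB) phase ends. It ends PT, "for subjects who entered OL phase, the day of OL start date (defined below"), on that day. For every other subject PT ends at the later of the last PT visit and the end of trial. Protocol 6.4 sets who moves on: "Subjects who relapse within 20 weeks after the start of the posttreatment phase will transit to an OL induction phase".

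SAP 5.1 also has one table split by time: "TEAEs will be summarized by onset time (4 week intervals"). It does not say whether each interval's denominator is the subjects still in the phase. Neither document specifies subject-time, exposure-adjusted incidence or time to first AE for PT.

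**The concern.** A crude percentage compares arms fairly when they are observed for about the same time. The two induction phases and the two follow-up phases are each nominally 4 weeks, so the measure suits them reasonably well. PT lasts up to 24 weeks, and for most relapsers its length is fixed by relapse, the outcome the phase is there to measure. The SAP allows for unequal follow-up when it analyses relapse itself (Kaplan-Meier with censoring, SAP 4.3.3) but not when it counts AEs in the same subjects.

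The stake is how the PT table is read. The safety objectives compare esketamine with placebo, including effects after stopping treatment. An arm whose responders stay well longer is watched longer and can accumulate more subjects with an event for that reason alone. This mechanism is separate from the selection of responders into PT and would operate even if the responders in each arm were exchangeable.

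**Working it through.** **Window length, from the plan.** The SAP's own target day reproduces: Week x of PT is Day 25 + 7x (SAP Table 1), so Week 24 is 25 + 7 × 24 = Day 193.

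- PT start: DB ends on Day 28, so Day 29.
- Shortest window for a relapser entering OL: the last DB dose is on Day 25 and OL may start 14 days later (Protocol 6.4.1), so Day 39. 39 − 29 + 1 = 11 days (9 to 13 with visit windows).
- Longest such window: relapse by 20 weeks, Day 168. 168 − 29 + 1 = 140 days, or up to 146 because OL must start before the next weekly MADRS.
- Full window: 193 − 29 + 1 = 165 days (161 to 169 with visit windows).

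The ratio of longest to shortest is 165/11 = 15.

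**Size of the distortion, from assumptions.** The documents give no PT relapse or AE rate. Assume the same constant AE hazard *h* in both arms, a constant relapse hazard *l* from Day 39 giving cumulative relapse *p* at Day 193, independence of the two, and exit from PT at relapse. The exposed time is 11/7 weeks plus 154/7 = 22 weeks.

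- *l* = −ln(1 − *p*)/22
- Mean weeks in PT = 11/7 + (1 − e^(−22*l*))/*l*
- Crude proportion = 1 − e^(−11*h*/7) + e^(−11*h*/7) × *h*/(*h*+*l*) × (1 − e^(−22(*h*+*l*)))
- For a 40% risk over 165 days (23.57 weeks), *h* = −ln(0.6)/23.57 = 0.0217 per week

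Example, *p* = 30%: *l* = 0.0162, so mean time is 1.57 + 0.30/0.0162 = 20.1 weeks. The crude proportion is 0.0335 + 0.9665 × 0.572 × 0.565 = 34.6%.

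| Relapse, arm A vs B | Mean weeks in PT | Crude AE % | Gap (points) |
|---|---|---|---|
| 50% vs 60% | 17.4 vs 16.0 | 30.5 vs 28.2 | 2.3 |
| 40% vs 60% | 18.8 vs 16.0 | 32.6 vs 28.2 | 4.4 |
| 40% vs 70% | 18.8 vs 14.4 | 32.6 vs 25.7 | 6.9 |
| 30% vs 80% | 20.1 vs 12.5 | 34.6 vs 22.7 | 11.9 |

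In every row the true rate is equal: 0.31 per 100 subject-days in both arms.

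**Varying the assumptions, at 30% vs 80% relapse.**

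- Full-window AE risk of 20%: 17.2% vs 10.9%. Risk of 60%: 52.6% vs 35.8%.
- First 4-week interval only (40% case): 8.2% vs 7.9%, almost no distortion.
- All AE risk (40%) in the first 28 days: 39.6% vs 38.3%, a gap of 1.3 points.

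**The case against.** The strongest reply is that this is a descriptive, off-drug table in a Phase 2 study and that other planned outputs already reveal the imbalance.

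- The post-cessation questions (withdrawal, rebound, abuse liability) are placed in the first 4 weeks of PT (Protocol 3.1). Distortion there is slight.
- SAP 3.3 summarises oral antidepressant exposure by phase, and relapse curves are given by arm. A careful reader could see unequal follow-up. This stands in part: the exposure table is split by drug, its top category is more than 28 days, and nothing links it to the AE table.
- The 4-week onset table helps. Its first interval is almost unbiased, but later intervals are not unless the denominator is the subjects still in PT, which is not stated.
- Protocol 11.8 names the safety data of the DB period and of OL induction, not PT, and no test of PT adverse events is planned. AEs after OL start are not lost; they are counted in the OL phase. Both points are right, though the OL count does not repair the PT comparison.
- Numbers will be small. If 20% to 50% of 37 subjects respond (an assumption), a dose arm has about 7 to 18 subjects in PT, so one subject is 100/18 = 5.6 to 100/7 = 14.3 points. A gap of 2 to 12 points is then about two subjects at most.

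A reader might also infer that the worst Columbia Suicide Severity Rating Scale (C-SSRS) score is distorted in the same direction, since SAP 5.5.1 takes "Shifts from the baseline visit to the most severe/maximum score during each analysis phase". The documents do not support that. Relapse itself includes suicide attempt, completed suicide and hospitalisation to prevent suicide (SAP 4.3.3.1). Such events fall inside PT because OL cannot start before relapse, so faster relapse could raise the maxima. SAP 5.5.1 also plans frequencies at each scheduled visit. For the same reason, the independence assumed above should not be applied to suicide-related AEs.

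**Conclusion.** The point holds in a limited form. PT adverse events are reported as crude percentages over windows that vary about 15-fold and depend on relapse, with no subject-time or at-risk denominator specified. Under equal constant hazards and a 40% full-window risk, the spurious gap is about 2 to 12 points across the relapse differences tried, and about 1 point if events cluster early. Both the direction and the size depend on relapse timing differing by arm and AE risk persisting through PT. Neither is known from the documents.

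Three stronger readings are tempting and should be resisted:

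- The window does not close at relapse for every subject. It closes at OL start, and only for those who enter OL. Relapsers barred from OL because they relapse within 14 days of the last DB dose keep a PT window to the later of the last PT visit and end of trial (SAP 2.1.2). The calculation does not model them.
- The other phases are not strictly fixed at 4 weeks. DB and OL induction end at completion or withdrawal, and 12.5% drop-out is assumed. PT differs in degree and in its link to relapse.
- It does not follow that the faster-relapsing arm will look safer, or that the PT percentages are unusable. They need follow-up time beside them.

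The primary analysis and the induction-phase safety tables are unaffected.

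**What to change.** In SAP 5.1, for the PT phase only:

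1. Beside each crude percentage, give exposure-adjusted incidence by arm: subjects with the event divided by subject-weeks from PT start to the first event, OL start or PT end, whichever comes first.
2. Show total PT subject-weeks per arm in the table header.
3. In the 4-week onset table, use subjects still in PT at the start of each interval as the denominator.

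No change to the C-SSRS summaries is needed on this ground. The cost is a few lines of SAP text and some table columns. All the dates are already derived, and no new data, visits or subjects are needed. The drawback is that a rate per subject-week assumes a roughly constant hazard and will be imprecise in small responder subsets, so the crude percentages should stay.
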